5.2.4 Electrocardiogram

The 12-lead ECGs must be administered by a qualified technologist and results will be recorded as scheduled in the [Flow Chart](#). The investigator or a designee will evaluate whether the ECG is normal or abnormal and assess clinical relevance. ECGs may be repeated for quality reasons and a repeated recording used for analysis. Additional ECGs may be recorded for safety reasons. Dated and signed printouts of ECG with findings should be documented in patient's medical record.

Clinically relevant abnormal findings will be reported either as baseline condition (if identified at Visit 1) or otherwise as AEs and will be followed up and/or treated as medically appropriate.

5.2.5 Other safety parameters

5.2.5.1 Malignancies

All cases of malignancies that are detected during the trial will be reported as SAEs. Patients with a documented active or suspected malignancy (except for specific cancers) will be excluded from this trial per the exclusion criteria ([Section 3.3.3](#)).

5.2.5.2 Columbia-Suicide Severity Rating Scale (C-SSRS)

Considering the characteristics of spesolimab, no penetration of blood-brain-barrier is anticipated, and a central effect triggering suicidal events is considered unlikely. The available pre-clinical and clinical data do not indicate effects of spesolimab on the central nervous system.

Pro-active screening for SIB in the HS clinical development program will be implemented with the following objectives:

- As a safety measure to exclude subjects at risk of suicidality and monitor for signs of suicidality.
- Structured data collection that may help in future assessment of potential signals around suicidality.

The C-SSRS is a semi-structured, investigator-rated interview, developed by clinical experts in cooperation with the FDA, assessing both suicidal behaviour and suicidal ideation. It does not give a global score, but provides some categorical and some severity information specifically for behaviour and ideation.

The C-SSRS interview may be administered by any type of physician, psychologist, clinical social worker, mental health counsellor, nurse, or coordinator with C-SSRS training. It has a typical duration of five minutes, and causes only a low burden on subjects. At a minimum, the interview consists of 2 screening questions related to suicidal ideation and 4 related to suicidal behaviour, and may be expanded to up to 17 items in case of positive responses. The investigator has to directly evaluate the scale and confirm that they evaluated and reviewed the scale. The investigator documents their evaluation and review of the scale by either,

- writing a statement in the source notes, or
- writing “reviewed” on questionnaire, signs, and dates the questionnaire.

The C-SSRS has been widely used in large multinational clinical trials. The C-SSRS will be administered at Visit 1 (using the ‘since last visit’ version) with the aim to exclude subjects with active moderate or severe symptomatology within a specified time prior to the baseline visit. The life time history of SIB will also be recorded.

After the baseline visit the assessment ‘since last visit’ will be performed at each clinic or phone visit (‘since last visit’ version). The investigator is to review positive and negative reports for plausibility and clinical relevance. Doubtful reports may be repeated or reports may be validated by a consulting psychiatrist. If there is a confirmed positive report of suicidal behaviour or suicidal ideation type 4 or 5 after start of trial, the investigator is to immediately interview the subject during the clinic visit, and/or is to consult a psychiatrist. If

the positive report is confirmed, appropriate actions for the subject's safety have to be initiated.

All C-SSRS reports of suicidal ideation type 4 or 5 and all reports of suicidal behaviour must be reported as SAEs by the investigator. For 'Self-injurious behaviour, no suicidal intent' (Type 11) standard AE / SAE reporting rules are to be applied. For each negative report (suicidal ideation type 1, 2 or 3) after start of the trial, the investigator is to decide based on clinical judgment whether it represents an AE as defined in the CTP, and if it is considered an AE then it must be reported accordingly.

5.2.5.3 Local Tolerability

Local tolerability at the administration site of spesolimab will be assessed by the investigator during the trial drug administration visit and at the time of AE assessment by questioning retrospectively since the last visit. Any observed local tolerability reaction, e.g. "swelling", "induration", "heat", "redness", "pain", and any other findings should be reported as AEs (see [Section 6.2.2](#)).

5.2.6 Assessment of adverse events

5.2.6.1 Definitions of AEs

5.2.6.1.1 Adverse event

An AE is defined as any untoward medical occurrence in a patient or clinical investigation subject administered a medicinal product and which does not necessarily have to have a causal relationship with this treatment.

An AE can therefore be any unfavourable and unintended sign (including an abnormal laboratory finding), symptom, or disease temporally associated with the use of a medicinal product, whether or not considered related to the medicinal product.

The following should also be recorded as an AE in the CRF and BI SAE form (if applicable):

- Worsening of the underlying disease or of other pre-existing conditions
- Changes in vital signs, ECG, physical examination and laboratory test results, if they are judged clinically relevant by the investigator.

If such abnormalities already exist prior to trial inclusion, they will be considered as baseline conditions and should be collected in the electronic case report form (eCRF) only. However, if these abnormalities are AEs of the parent PoCC trial and still ongoing after the first dose in this extension trial, then they should not be recorded as baseline conditions. In such situations [Section 5.2.6.2](#) should be followed.

5.2.6.1.2 Serious adverse event

A SAE is defined as any AE, which fulfils at least one of the following criteria:

- results in death,

- is life-threatening, which refers to an event in which the patient was at risk of death at the time of the event; it does not refer to an event that hypothetically might have caused death if more severe,
- requires inpatient hospitalisation or prolongation of existing hospitalisation
- results in persistent or significant disability or incapacity,
- is a congenital anomaly / birth defect,
- is deemed serious for any other reason if it is an important medical event when based on appropriate medical judgement which may jeopardise the patient and may require medical or surgical intervention to prevent one of the other outcomes listed in the above definitions. Examples of such events are intensive treatment in an emergency room or at home for allergic bronchospasm, blood dyscrasias or convulsions that do not result in hospitalisation or development of dependency or abuse.

5.2.6.1.3 AEs considered “Always Serious”

In accordance with the European Medicines Agency initiative on Important Medical Events, BI has set up a list of AEs, which by their nature, can always be considered to be “serious” even though they may not have met the criteria of an SAE as defined above.

The latest list of “Always Serious AEs” can be found in the eDC system. A copy of the latest list of “Always Serious AEs” will be provided upon request. These events should always be reported as SAEs as described in [Section 5.2.6.2](#).

Cancers of new histology and exacerbations of existing cancer must be classified as a serious event regardless of the time since discontinuation of the drug and must be reported as described in [5.2.6.2](#), subsections “AE Collection” and “**AE reporting to sponsor and timelines**”.

5.2.6.1.4 Adverse events of special interest

The term AESI relates to any specific AE that has been identified at the project level as being of particular concern for prospective safety monitoring and safety assessment within this trial, e.g. the potential for AEs based on knowledge from other compounds in the same class. AESIs need to be reported to the sponsor’s Pharmacovigilance Department within the same timeframe that applies to SAEs, please see [Section 5.2.6.2.2](#).

The following are considered as AESIs:

Systemic hypersensitivity including infusion reaction and anaphylactic reaction

Any suspicion of severe infusion reaction systemic / hypersensitivity reaction and of any potential cases of anaphylaxis should be defined and assessed using the criteria discussed in the statement paper from Sampson HA ([Appendix 10.1 \[R11-4890\]](#)).

Severe infections

Refer to the RCTC grading in the ISF.

Opportunistic and mycobacterium tuberculosis infections

These include pneumocystis jirovecii, BK virus disease including PVAN, CMV, post-transplant lymphoproliferative disorder (EBV), progressive multifocal leucoencephalopathy, bartonellosis (disseminated only), blastomycosis, toxoplasmosis, coccidioidomycosis, histoplasmosis, aspergillosis (invasive only), candidiasis (invasive or pharyngeal), cryptococcosis, other invasive fungi (mucormycosis (zygomycosis, rhizopus, mucor, lichtheimia), scedosporium/pseudallescheria boydii, fusarium), legionellosis, listeria monocytogenes (invasive only), TB, nocardiosis, non-tuberculous mycobacterium, salmonellosis (invasive only), HBV reactivation, herpes simplex (invasive only), herpes zoster, strongyloides (hyperinfection syndrome and disseminated forms only), paracoccidioides, penicillium marneffeii, sporothrix schenckii, cryptosporidium species (chronic only), microsporidiosis, leishmaniasis (visceral only), trypanosoma cruzi infection (Chagas' disease) (disseminated only), campylobacteriosis (invasive only), shigellosis (invasive only), vibriosis (invasive due to vibrio vulnificus), hepatitis C virus progression [[R17-2617](#)].

Potential Severe DILI

A potential severe Drug Induced Liver Injury (DILI) that requires follow-up is defined by the following alterations of hepatic laboratory parameters:

- An elevation of AST (Aspartate Aminotransferase) and / or ALT (Alanine Aminotransferase) ≥ 3 -fold ULN combined with an elevation of total bilirubin ≥ 2 -fold ULN measured in the same blood sample, or in samples drawn within 30 days of each other; or
- ALT and / or AST elevations ≥ 10 -fold ULN.

These lab findings constitute a hepatic injury alert and the patients showing these lab abnormalities need to be followed up according to the "DILI checklist" provided in the ISF.

In case of clinical symptoms of hepatic injury (icterus, unexplained encephalopathy, unexplained coagulopathy, right upper quadrant abdominal pain, etc.) without lab results (ALT, AST, total bilirubin) available, the investigator should make sure these parameters are analysed, if necessary, in an unscheduled blood test. Should the results meet the criteria of hepatic injury alert, the procedures described in the DILI checklist should be followed.

For patients with abnormal aminotransaminase levels between >1 and <3 x ULN at baseline:

1. An elevation of AST and / or ALT ≥ 3 -fold the baseline value combined with an elevation of bilirubin ≥ 2 -fold ULN or ≥ 2 -fold the baseline value (if bilirubin is elevated at baseline), measured in the same blood sample, or in samples drawn within 30 days of each other, or,
2. Aminotransferase elevations ≥ 5 -fold the baseline value.

For patients with abnormal aminotransaminase levels between ≥ 3 x ULN and <5 x ULN at baseline:

1. An elevation of AST and / or ALT ≥ 2 -fold the baseline value combined with an elevation of bilirubin ≥ 2 -fold ULN or ≥ 2 -fold the baseline value (if bilirubin is elevated at baseline); measured in the same blood sample or in samples drawn within 30 days of each other, or,
2. Aminotransferase elevations ≥ 3 -fold the baseline value.

Peripheral Neuropathy Any event suspected or diagnosed as Peripheral Neuropathy would be considered as an AESI. For the treatment interruption rules, please see [Section 4.2.1.4](#).

5.2.6.1.5 Intensity (severity) of AEs

The intensity (severity) grading of AEs will be performed according to RCTC Version 2.0 developed by the Outcome Measures in Rheumatology organization [[R13-3515](#)]. Refer to the ISF for intensity/severity classification.

Intensity options are:

Grade 1	mild
Grade 2	moderate
Grade 3	severe
Grade 4	life-threatening.

5.2.6.1.6 Causal relationship of AEs

Medical judgement should be used to determine whether there is a reasonable possibility of a causal relationship between the adverse event and the given study treatment, considering all relevant factors, including pattern of reaction, temporal relationship, de-challenge or re-challenge, confounding factors such as concomitant medication, concomitant diseases and relevant history.

Arguments that may suggest that there is a reasonable possibility of a causal relationship could be:

- The event is consistent with the known pharmacology of the drug.
- The event is known to be caused by or attributed to the drug class.
- A plausible time to onset of the event relative to the time of drug exposure.
- Evidence that the event is reproducible when the drug is re-introduced.
- No medically sound alternative aetiologies that could explain the event (e.g. pre-existing or concomitant diseases, or co-medications).
- The event is typically drug-related and infrequent in the general population not exposed to drugs (e.g. Stevens-Johnson syndrome).
- An indication of dose-response (i.e. greater effect size if the dose is increased, smaller effect size if dose is reduced).

Arguments that may suggest that there is no reasonable possibility of a causal relationship could be:

- No plausible time to onset of the event relative to the time of drug exposure is evident (e.g. pre-treatment cases, diagnosis of cancer or chronic disease within days / weeks of drug administration; an allergic reaction weeks after discontinuation of the drug concerned).
- Continuation of the event despite the withdrawal of the medication, taking into account the pharmacological properties of the compound (e.g. after 5 half-lives).
Of note, this criterion may not be applicable to events whose time course is prolonged despite removing the original trigger.

- Additional arguments amongst those stated before, like alternative explanation (e.g. situations where other drugs or underlying diseases appear to provide a more likely explanation for the observed event than the drug concerned).
- Disappearance of the event even though the trial drug treatment continues or remains unchanged.

5.2.6.2 Adverse event collection and reporting

5.2.6.2.1 AE Collection

The investigator shall maintain and keep detailed records of all AEs in the patient files. The following must be collected and documented on the appropriate CRF(s) by the Investigator (special notes on SAE form reporting where needed):

- From the time of the signing of the consent form in the extension trial until the end of the EoS visit all AEs (serious and non-serious) and all AESIs.
- All AEs that started in the 1368-0052 PoCC (parent) trial (onset date in parent trial) and are still ongoing after 1st IMP administration in the extension trial:
- Re-record the AE in the extension trial eCRF with the same information as it was recorded in the parent trial.
- Should the AE end during the course of the extension trial,
 - ⇒ update both - the extension trial eCRF and the parent trial eCRF. If the parent trial is already locked, update only the extension trial eCRF. In this case the update for the parent trial will be handled outside of the eCRF of the parent trial.
- However, concerning reporting on the SAE form (if applicable), the follow-up report will still be sent on the parent trial SAE form, no new SAE form is to be completed for the extension trial.
- If the intensity of an ongoing AE changes after 1st IMP administration in the extension trial:
 - ⇒ update both - the extension trial eCRF and the parent trial eCRF- with the end date for the initial/previous intensity. If the parent trial is already locked, update only the extension trial eCRF. In this case the update for the parent trial will be handled outside of the eCRF of the parent trial.
 - ⇒ The AE with the new intensity will be handled as new event; this means it is only recorded in the extension trial eCRF.
 - ⇒ Example: If the intensity increased then the new AE name/term should contain “Worsening of...” or “Exacerbation of...”.

Considerations for reporting on the SAE form, when intensity change qualifies as worsening/exacerbation of an event that had already been reported on the SAE form:

- corresponding follow up report to be sent on the parent trial SAE form with date of worsening as event end date.
- extension trial SAE form to be sent as initial report for the extension trial for new event “worsening/exacerbation of...” with date of worsening as onset date.

Considerations for reporting on the SAE form, when intensity change qualifies as worsening/exacerbation of an event and requires for the first time reporting on the SAE form (meeting for the first time seriousness/AESI criteria):

- only extension trial SAE form to be sent - as initial report for the extension trial for new event “worsening/exacerbation of...” with date of worsening as onset date.

- All AEs with an end date **before** the 1st IMP administration in the extension trial, even if Informed Consent of the extension trial was already signed:
 - Record only in the eCRF of the parent trial.
 - In case of an AE reportable on the SAE form, send the update only on the SAE form of the parent trial.
 - Do not re-record in the extension trial eCRF, do not complete a new SAE form for the extension trial.
- After the EoS visit in the extension trial:

After a patient’s EoS Visit in the extension trial the investigator does not need to actively monitor the patient for new AEs but should only report new malignancies or the exacerbation of existing malignancies, trial treatment related SAEs and trial treatment related AESIs of which the investigator may become aware of by any means of communication, e.g. phone call. Those AEs should be reported on the BI SAE form (see [Section 5.2.6.2.2](#)) for the extension trial, but not on the CRF (neither on CRF for extension trial nor for parent trial).

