7.2.5 Safety analyses

Adverse events will be coded using the Medical Dictionary for Drug Regulatory Activities (MedDRA). Standard BI summary tables and listings will be produced. All adverse events with an onset between start of treatment and end of the REP, (i.e., 16 weeks after last study treatment) will be assigned to the on-treatment period for evaluation.

All treated patients will be included in the safety analysis. In general, safety analyses will be descriptive in nature and will be based on BI standards. No hypothesis testing is planned.

Statistical analysis and reporting of adverse events will concentrate on treatment-emergent adverse events, i.e. all adverse events occurring between start of the first treatment and end of the REP of the last treatment. Adverse events that start before first drug intake and deteriorate under treatment will also be considered as 'treatment-emergent'. Safety assessments including treatment emergent adverse events, laboratories, vital signs etc. based on SAF.

Frequency, severity, and causal relationship of treatment emergent adverse events will be tabulated by system organ class (SOC) and preferred term after coding according to the current version of the MedDRA at DBL. Exposure adjusted incidence rate of all treatment emergent adverse events will also be presented.

The exposure adjusted incidence rate (per 100 subject years) of a selected treatment emergent adverse event is defined as the number of subjects experiencing the adverse event per treatment group during time at risk divided by the total time of subjects at risk in that treatment group to contribute the event to the analysis multiplied by 100 (per 100 subject year), where:

$$\text{Time at risk [subject years]} = (\text{date of onset of TEAE} - \text{study drug start date} + 1) / 365.25$$

If, for a subject, the selected treatment emergent adverse event didn't occur then the time at risk will be censored at min (date of death, last contact date per EoS page, drug stop date + 112 days, cut-off date if interim analysis performed). For each selected treatment emergent AE, the exposure adjusted incidence rate will be calculated as:

$$\text{Incidence rate [1/100 Subject years (pt-yrs)]} = 100 * \text{number of subjects with TEAE} / \text{Total TEAE-specific time at risk [subject years]}.$$

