7.8.1 Adverse Events

AEs will be coded with the most recent version of MedDRA.

For AEs in current trial, we will summarize AEs start in 1368-0052 and still ongoing in current trial 1368-0067 plus new AEs start in current trial.

The analyses of AEs will be descriptive in nature. All analyses of AEs will be based on the number of patients with AEs and not on the number of AEs. System organ classes (SOC, if applicable) will be sorted according to the standard sort order specified by the EMA, preferred terms (PT, if applicable) will be sorted by total frequency (within SOC).

For details on summarization of AE data, please refer to "Handling and summarization of adverse event data for clinical trial reports and integrated summaries" ([15](#)) and "Handling of missing and incomplete AE dates" ([10](#)).

The analysis of AEs will be based on the concept of TEAEs. This means that all AEs will be assigned to the screening period, on-treatment period (i.e. treatment phase plus REP) or off-treatment period (i.e. follow up) as defined in [Section 6.1](#). Since only the start date of an AE is collected (without start time), any AE occurrence on the same day as the first spesolimab administration will be assigned to the on-treatment phase.

Exposure-adjusted adverse event incidence rates for TEAE will be calculated using the following approach:

- 1) The exposure adjusted incidence rate (per 100 subject years) of a selected TEAE is defined as the number of subjects experiencing the adverse event per treatment group during time at risk divided by the total time of subjects at risk to contribute the event to the analysis multiplied by 100 (per 100 subject years), where:

Time at risk [subject years] = (date of onset of AE – first treatment start date in current study +1) / 365.25

- 2) If, for a subject, the selected TEAE didn't occur, then the time at risk will be censored at min (date of death, last contact date per EoS page, cut-off date for the interim analysis, or the end of on-treatment period). For each selected TEAE, the exposure adjusted incidence rate will be calculated as:

Incidence rate [1/100 Subject years (pt-yrs)] = 100 * number of subjects with TEAE / Total TEAE-specific time at risk [subject years].

An overall summary of AEs will be presented. This overall summary will include summary statistics for the class of other significant AEs (sponsor definition based on ICH E3) and for the class of AESIs.

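### A parent-trial AE that eases after first dose is handled as a new event and, by its implied onset date, qualifies as a TEAE, although Protocol 7.2.5 brings in earlier-starting AEs through deterioration

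*Protocol*

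**What the plan says.** Protocol 5.2.6.2.1 has AEs that began in 1368-0052 and are still ongoing after the first dose re-recorded unchanged in the extension eCRF. A further rule starts with "If the intensity of an ongoing AE changes after 1st IMP administration in the extension trial". The existing record is then closed "with the end date for the initial/previous intensity", and "The AE with the new intensity will be handled as new event", which the protocol explains as entering it in the extension eCRF alone. An increase appears only as a naming illustration: "Example: If the intensity increased then the new AE name/term should contain" a word for worsening or exacerbation. An explicit onset date, "with date of worsening as onset date", is given only in the SAE-form rules, and only for worsening.

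On the analysis side, the primary endpoint is the occurrence of TEAEs (Protocol 2.1.2). Protocol 7 puts into its primary analysis every AE whose onset lies between start of treatment and end of the residual effect period. Protocol 7.2.5 adds "Adverse events that start before first drug intake and deteriorate under treatment" as treatment-emergent. SAP 7.8.1 assigns each AE to the screening, on-treatment or off-treatment period, with the start date as the only timing collected. It counts patients, not events. It also says the summaries will cover parent-trial AEs still ongoing in this trial as well as new ones.

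**The concern.** The recording rule and the TEAE definition treat an improving AE differently. As one continuous event, an AE that began in the parent trial and goes from moderate to mild after first dose does not meet the deterioration clause in Protocol 7.2.5. Once it is split, the mild portion is a separate event that appears to start on treatment, and the onset rule admits it.

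Long-term safety is the primary objective, so what counts as treatment-emergent matters. In a preferred-term table, a patient who is recovering can appear as a patient with an AE on spesolimab. In an exposure-adjusted rate, the same record adds an event and also ends that patient's time at risk early.

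**Working it through.** The plan states no sample size, power or alpha calculation, so there is no figure to reproduce. The check is a reading of the rules in sequence, followed by illustrative arithmetic.

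**Reading**

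1. *Trigger.* Any change of intensity, with no direction stated. The SAE-form paragraphs in the same section are limited to worsening; the eCRF rule is not.
2. *Record.* The old intensity is end-dated and the new intensity becomes a separate event. Protocol 8.3.1 makes an AE onset date mandatory, so the new record needs one. The natural date is that of the change, after first dose.
3. *Classification.* Protocol 7 and SAP 7.8.1 go by onset. Neither excludes a record created by a decrease.
4. *Comparison.* Protocol 7.2.5 reaches AEs that began before first drug intake through deterioration. Easing is not deterioration.

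**Incidence**

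Input: about 45 patients (Protocol synopsis). If k patients appear under a preferred term only because of an eased AE, the added incidence is k/45:

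- k = 1: 1/45 = 2.2 points
- k = 3: 3/45 = 6.7 points
- k = 5: 5/45 = 11.1 points

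Columns by prior treatment have smaller denominators, which the documents do not give. For an assumed group of 15, one patient is 1/15 = 6.7 points; for an assumed 30, it is 1/30 = 3.3 points.

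These are ceilings. If the patient is already counted under that term because the ongoing parent-trial AE is itself summarised, the addition is 0.

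**Exposure-adjusted rate**

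Formula (Protocol 7.2.5, SAP 7.8.1): rate = 100 × patients with the event / total time at risk in years. Time at risk ends at onset.

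Assumptions: 104 weeks of treatment (the documents say 2 years; the exact number of weeks is not visible) plus 112 days, giving F = (728 + 112)/365.25 = 2.30 years; full follow-up for everyone else; a true cases, each at mid-follow-up; k eased AEs, each split at day 28 (28/365.25 = 0.077 years).

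Time at risk = (45 − a − k) × F + a × F/2 + k × 0.077

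| True cases a | k = 0 | k = 1 | k = 3 |
|---|---|---|---|
| 0 | 0.00 | 0.99 | 3.10 |
| 2 | 1.98 | 3.03 | 5.29 |
| 5 | 5.12 | 6.28 | 8.78 |

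(per 100 subject-years)

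For a = 2, k = 1: 42 × 2.2998 + 2.2998 + 0.077 = 98.97 years, and 300/98.97 = 3.03.

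The k = 0 column takes the unsplit parent-trial AE as no event in the rate. An onset before first dose gives zero or negative time at risk in the formula, so it cannot properly enter. The split record supplies a date that does.

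**The case against.** The strongest objection is that SAP 7.8.1 already summarises parent-trial AEs still ongoing and counts patients rather than events. If the carried-over AE is in the table, a second record of it at lower intensity adds nobody. That stands for incidence: a reader might infer that every eased AE adds 2.2 points to its preferred term, and the SAP as written does not support that. It does not settle the exposure-adjusted rates, which need an on-treatment onset date, nor the onset-based primary analysis in Protocol 7, which does not mention ongoing parent-trial AEs.

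Second, the new-event wording can be read as a routing instruction, since the protocol explains it by saying which eCRF to use. The on-treatment onset for a decrease is indeed inferred and not written, and a site could enter another date. But end-dating the old intensity and opening a new event leaves the date of change as the natural onset.

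Third, Protocol 7.2.5 is an inclusion clause without the word only. A reader might infer that it expressly bars eased AEs; it does not. Deterioration is, however, the only route it gives for AEs that began earlier.

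Fourth, the SAP defers detail to sponsor AE-handling standards outside the documents. These might collapse successive records of one AE. Neither the protocol nor the SAP says so.

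Fifth, an overcount of AEs errs on the cautious side in a descriptive trial, and only carried-over AEs above grade 1 can ease to a lower grade. Both points are fair and limit the weight of the issue.

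**Conclusion.** The conflict is real: the recording rule in Protocol 5.2.6.2.1 reaches further than the treatment-emergence rule in Protocol 7.2.5, and nothing in the onset-based analysis rules closes the gap.

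Its size is modest and uncertain. Overall incidence for a preferred term moves by between 0 and 2.2 points per affected patient. The exposure-adjusted rate of a sparse term can move more in relative terms (1.98 to 3.03 per 100 subject-years with one eased AE, under the assumptions above). The number of carried-over AEs that ease is not given, so no total can be stated.

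Two wider readings are not supported. The proportion with any TEAE would change little, because it moves only for patients with no other TEAE over about 2 years. Nor are all AESI classes inflated: a severe infection that eases below severe no longer meets that class, although classes not defined by grade could still be affected.

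**What to change.** - **Protocol 5.2.6.2.1:** limit the new-event rule to increases in intensity. For a decrease, keep the original record and its onset date.
- **SAP 7.8.1:** for data already collected, state that a record continuing a parent-trial AE is treatment-emergent only if its intensity exceeds that at first dose in this trial, and is otherwise listed only.
- **SAP 7.8.1, same edit:** reconcile this with the sentence on still-ongoing parent-trial AEs, saying whether those enter the TEAE tables and the rates or are shown separately.

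The cost is one protocol sentence (or eCRF completion instruction), one derivation rule and some record matching. The protocol describes no field linking a re-recorded AE to its successor, so the two must be paired by term and by end and start date, or by medical review. No extra data need be collected: re-recording already places the predecessor in the extension eCRF.
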